# 9.2.8. Patients on greater than 4mg per day of dexamethasone within the 2 weeks prior to admission for PVSRIPO infusion

[figure not shown]
- 9.2.9. Patients with worsening steroid myopathy (history of gradual progression of bilateral proximal muscle weakness, and atrophy of proximal muscle groups)
- 9.2.10. Patients with prior, unrelated malignancy requiring current active treatment with the exception of cervical carcinoma in situ and adequately treated basal cell or squamous cell carcinoma of the skin

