#### 14.3.1. Dose Expansion at Dose Level "-1"

Accrual at dose level -1 will be extended in order that a sufficient number of patients will be treated at that dose level to estimate its efficacy relative to a historical cohort.

As of 6/15/2015, 28 patients have been treated on this protocol, including 13 patients treated at dose level -1. The median survival is 15.2 months (95% confidence interval: 7,  $\infty$ ). Median follow-up among patients treated at dose level -1 is 3.5 months.

Informal comparisons of survival associated with PVSRIPO (including all patients at all dose levels) relative to that observed in other recurrent WHO grade IV malignant glioma patient groups suggest a hazard ratio in the ballpark of 0.5 to 0.65.

The historical cohort that will be used for this comparison will include recurrent WHO grade IV malignant glioma patients in the PRoGREss registry (IRB# Pro00027120; Primary and Recurrent Glioma Registry) who would have been eligible to receive PVSRIPO if the treatment had been available. Details about the construction of this comparison group, as well as a summary of control group patient characteristics are provided in Appendix 18.4. Two control groups were generated, with one group having no limit to pre-treatment steroid usage, and the other group having a steroid limit of  $\leq$  4 mg per day of dexamethasone within the 2 weeks prior to being eligible for PVSRIPO infusion. The first control group has eligibility criteria similar to that which was in existence for dose levels 1-5 and the first 5 patients on dose level "-1". The second control group has eligibility criteria similar to those currently being used for dose level "-1". The first historical control group includes 124 patients of which 123 are dead; whereas, the second historical control group includes 104 patients of which 103 are dead.

Korn and Friedlin (48) recommend the use of an unconditional power estimator for the determination of sample size in single arm studies that compare time-to-event outcomes such as survival with that observed in a historical control group. That estimator resembles an estimator for a 2-arm randomized study. The power of such a comparison is dependent upon the total number of observed deaths (49).

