Given that the study is not a randomized study, there is a need to statistically adjust survival comparisons for confounding factors. Hence, survival comparisons will be conducted using the Cox model. Predictors within the Cox model will include treatment, age, extent of resection, prior bevacizumab treatment, Karnofsky performance status at the time of PVSRIPO treatment, number of prior recurrences, and an indicator of secondary GBM.

It should be noted that the calculations and analyses described above assume that survival with PVSRIPO is exponentially distribution and that the proportional hazards assumption is satisfied. Recently reported studies suggest that such properties may not exist for immunotherapeutic agents due to (1) delayed antitumor effects and hence delayed separation of survival curves, and (2) a percentage of patients who are "cured" or survive for a relatively long period of time. If that is the situation with PVSRIPO, the power calculations and planned analyses may not be appropriate. It might be more appropriate to focus on long-term survivorship at a specific time point such as 18 and 24-month survival. Within the second historical control group, the 18 and 24-month survival probabilities are 23.1% and 13.5%, respectively. A two-tailed chi-square test ( $\alpha$ =0.2) conducted to compare the proportion of patients alive at 18 or 24 months at the 0.2 level has >84% power to detect an increase of 15% in survivorship. Logistic regression will be used to adjust for confounding factors.

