After the first 5 patients were treated at dose level "-1," the PVSRIPO WHO grade IV malignant glioma Phase I study was amended to institute a limit on pre-treatment steroid usage to  $\leq$  4 mg per day of dexamethasone within the 2 weeks prior to admission for PVSRIPO infusion. There were no steroid limitations for all patients treated on dose levels 1-5 and for the first 5 patients treated on dose level "-1". To address this eligibility amendment, two control groups have been generated, with one group having no limitations on pre-treatment steroid usage, and the other group having a steroid limit of  $\leq$  4 mg per day of dexamethasone (or equivalent) within the 2 weeks prior to being eligible for PVSRIPO infusion.

Within these historical control cohorts, survival time was computed as the time between the date of the first MRI at which time the patient would have been eligible to receive PVSRIPO and the date of death. If the patient remained alive at the date of last follow-up, survival time was censored at that date.

Characteristics of the Patients within the Historical Control Group: A summary of selected patient characteristics in these two historical control groups is provided below.

		Gro	oup		
Patient Characteristics	con with s	orical trols steroid led pts)	Historical controls (without steroid expanded pts)		
	Ν	%	Ν	%	
All	124	100.0	104	100.0	
Gender					
Female	44	35.5	39	37.5	
Male	80	64.5	65	62.5	
Histologic Diagnosis					
GBM	124	100.0	104	100.0	
Age at GBM Diagnosis, mean (SD)	55.3	(10.9)	54.7	(11.2)	
Age at GBM Diagnosis, median (range)	55 (20	) – 76)	54 (20	0 – 76)	
Primary or Secondary GBM					
Primary	110	88.7	92	88.5	
Secondary	13	10.5	11	10.6	
Unknown	1	0.8	1	1.0	
Karnofsky Performance Status					
100	8	6.5	8	7.7	
90	69	55.6	64	61.5	
85	2	1.6	2	1.9	
80	36	29.0	27	26.0	
70	7	5.6	2	1.9	
Undetermined but ≥70	2	1.6	1	1.0	
Resection Type at diagnosis*					
GTR	73	58.9	60	57.7	
STR	29	23.4	25	24.0	
Biopsy	22	17.7	19	18.3	
Further Surgery prior to Treatment**					
GTR	8	6.5	8	7.7	
STR	6	4.8	4	3.8	
None	110	88.7	92	88.5	
PDs prior to being eligible	102	82.3	85	81.7	

	Group						
Patient Characteristics	con with s(	orical trols steroid led pts)	Historical controls (without steroid expanded pts				
	Ν	%	Ν	%			
1							
2	14	11.3	12	11.5			
3	8	6.5	7	6.7			
Total Daily Dex (or other steroid) dose at MRI							
0	89	71.8	89	85.6			
0.125	1	0.8	1	1.0			
0.5	1	0.8	1	1.0			
1	1	0.8	1	1.0			
2	3	2.4	3	2.9			
4	8	6.5	8	7.7			

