6	2	1.6	0	0			
8	4	3.2	0	0			
12	4	3.2	0	0			
14	1	0.8	0	0			
16	3	2.4	0	0			
30 mg Hydrocortisone	1	0.8	1	1.0			
Unknown	6	4.8	0	0			
Avastin prior to eligible PD							
No	61	49.2	49	47.1			
Yes	63	50.8	55	52.9			
Avastin Failure prior to eligible PD							
No	75	60.5	61	58.7			
Yes	49	39.5	43	41.3			
Vital Status							
Alive	1	0.8	1	1.0			
Dead	123	99.2	103	99.0			

\*In both control groups, this includes 1 patient with a questionable STR/GTR, and 1 patient with a GTR on the primary tumor and a STR on a second tumor. \*\*In both control groups, this includes 1 patient with a questionable STR/GTR.

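### The Cox model for the dose level -1 survival comparison omits bevacizumab failure and baseline steroid dose, both tabulated for all 104 controls, so residual confounding of unknown size and direction is possible

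*Combined protocol and SAP*

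**What the plan says.** Section 14.3.1 accepts that, without randomisation, "there is a need to statistically adjust survival comparisons for confounding factors". It then names the model terms. Beyond treatment, age and resection extent, they are "prior bevacizumab treatment, Karnofsky performance status at the time of PVSRIPO treatment, number of prior recurrences, and an indicator of secondary GBM". That is seven terms. Bevacizumab appears only as prior treatment, which reads as yes or no. Steroid dose does not appear.

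Appendix 18.4 describes the controls and includes rows headed "Total Daily Dex (or other steroid) dose at MRI" and "Avastin Failure prior to eligible PD". In the second control group (104 patients, 103 dead), which section 14.3.1 selects for this comparison, neither row has an unknown value.

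That second group is restricted to at most 4 mg/day of dexamethasone, in line with the trial exclusion in section 9.2.8: "Patients on greater than 4mg per day of dexamethasone within the 2 weeks prior to admission for PVSRIPO infusion". Section 14.3.1 also says that the first, unrestricted control group resembles the eligibility in force for "dose levels 1-5 and the first 5 patients on dose level" -1. Those five patients are not removed from the comparison with the second group.

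For the 18- and 24-month survival comparisons (sections 14.3.1 and 14.3.2), the plan says logistic regression will adjust for confounders but lists none.

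**The concern.** Confounding is a main threat to a historical comparison, and the Cox list is the plan's stated tool against it once the control group has been chosen. Two measured baseline factors are left off. Having failed bevacizumab is a different clinical state from having received it, so a yes/no term treats two kinds of patient as one. Steroid dose mattered enough to the plan that it built a second control group around it.

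The question answered by the comparison is whether dose level -1 merits further study, at a one-sided 0.20 level. If the treated patients differ from the controls on either factor within the strata already adjusted for, the adjusted hazard ratio absorbs that difference.

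**Working it through.** **1. What the controls show (Appendix 18.4, second group, n = 104).**
- Steroids: 89 at zero; on any steroid 1 + 1 + 1 + 3 + 8 + 1 = 15, or 14.4%; none unknown (89 + 15 = 104).
- Prior bevacizumab: 55 (52.9%). Bevacizumab failure: 43 (41.3%). The two are not cross-tabulated. If every failure is a prior user, 43/55 = 78% of users failed and 12 were exposed without failure.
- Correlation of the two indicators on that assumption: phi = (43 × 49 − 12 × 0) / √(55 × 49 × 43 × 61) = 0.79. The yes/no term therefore carries much, but not all, of the failure information.

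**2. Steroid restriction.** Level -1 patients after the first five fall under the same 4 mg/day ceiling as the controls. The first five do not: 5/50 = 10% of the planned cohort.

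**3. Reproducing the plan's power.** With d treated deaths and 103 control deaths, V = 103d/(d + 103) and power = Φ(|ln HR|·√V − 0.842) at one-sided 0.20. For d = 15, V = 13.09, giving 0.952, 0.907, 0.843 and 0.763 at hazard ratios 0.5, 0.55, 0.6 and 0.65. Table 4, row 0, states 0.95, 0.91, 0.84 and 0.76, so it reproduces.

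**4. Can the Cox model carry two more terms?** Deaths run from 15 + 103 = 118 to 30 + 103 = 133 (Table 4, 0 and 12 months).
- Seven terms: 16.9 to 19.0 deaths per term.
- Nine terms: 13.1 to 14.8.
- Eleven terms, if some factors need extra categories: 10.7 to 12.1.

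Power cost, with V multiplied by (1 − R²), where R² is the added correlation with treatment (assumed), at d = 15:
- R² = 0.05: 0.946 at HR 0.5; 0.751 at HR 0.65.
- R² = 0.10: 0.938; 0.738.
- R² = 0.20: 0.919; 0.710.

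**5. Could the omission matter, and which way?** Treated-arm prevalence and prognostic strength are not in the documents, so this step is assumption throughout. For a factor with hazard ratio h and prevalence p1 (treated) and p0 (controls), the treatment hazard ratio is multiplied by roughly B = (p1·h + 1 − p1)/(p0·h + 1 − p0). B below 1 flatters PVSRIPO.
- Failure among prior users, p0 = 0.782, h = 1.25 to 2.0, p1 = 0.40 to 1.00. Extremes at h = 2: 1.40/1.782 = 0.79 and 2.00/1.782 = 1.12. Weighted by the controls' 52.9% prior use (assumed equal in the treated arm), exp(0.529·ln B) gives 0.88 to 1.06. At p1 = 0.782, B = 1.
- Any steroid, p0 = 0.144, h = 1.25 to 2.0, p1 = 0 to 0.50. Extremes at h = 2: 1/1.144 = 0.87 and 1.5/1.144 = 1.31.

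Both ranges straddle 1.

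**6. The logistic models.** Expected 24-month survivors at level -1: 104 × 0.135 + 50 × 0.135 = 20.8 with no effect, or 14.0 + 50 × 0.285 = 28.3 with a 15-point gain. At level -2: 14.0 + 27 × 0.135 = 17.7, or 14.0 + 27 × 0.35 = 23.5. Nine terms would leave 2.0 to 3.1 survivors per term. At 18 months (level -1) the corresponding figure is 4.0 to 4.8.

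**The case against.** Adjustment is not the plan's only protection. Appendix 18.4 selects controls by trial-like criteria (KPS of at least 70, tumour size, no rapid decline) with imaging reviewed blind to survival. Steroids are handled by a dedicated restricted group in which 85.6% take none. Prior bevacizumab is already in the model, and if treated users failed as often as control users, the yes/no term is enough. No imbalance has been shown. This is a phase I expansion with a lenient screening test, and the choice of covariates is partly a matter of judgement.

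Most of that stands, and it limits the point. It does not remove it. Restriction leaves dose variation below the ceiling and does not cover the first five patients. The yes/no term suffices only if the treated arm shares the controls' 78% failure share, and nothing in the documents says so.

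The cost objection also stands in part. Section 9.2.5 concerns the timing of earlier bevacizumab and recovery from side effects, not failure. Section 9.2.8 needs only a threshold check. Section 12.1 lists neither failure status nor steroid dose among the data to be collected. Treated-arm values would have to be extracted from records, and failure defined one way in both arms.

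**Conclusion.** The omission from the Cox list is plain on the page, the control data exist for all 104 patients, and the model has enough deaths to take the terms. Residual confounding is possible, and pre-specifying the terms is worthwhile.

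Three stronger readings are not supported:
- A reader might infer that the comparison is biased towards PVSRIPO, or that its false-positive rate is materially above 0.20. The documents give no treated-arm distribution of either factor, and the assumed ranges run in both directions. An error rate simulated for an unadjusted log-rank test would not describe the planned Cox model.
- A reader might infer that steroid exposure is uncontrolled. It is mostly controlled, by restriction.
- A reader might infer that the 18- and 24-month models share the omission. Their covariates are unspecified, which is a different gap.

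The figure of 43 failures among 55 users rests on failures being a subset of users. The power cost rests on an assumed R-squared.

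**What to change.** In the section 14.3.1 Cox model:
- Replace yes/no prior bevacizumab with three levels: none, received without failure, failed. State one definition of failure and apply it identically to trial patients and controls.
- Add baseline daily steroid dose in dexamethasone equivalents, converting the one control recorded on hydrocortisone.

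Add a sensitivity analysis that excludes the 5 level -1 patients treated without a steroid limit, or compares them with the first control group. Exclusion is the more informative choice: the alternative rests on five treated patients, and steroid dose is unknown for 6 of the 124 controls in that group.

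Do not add these terms to the 18- and 24-month logistic models. List a short covariate set for those, for both dose levels.

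This is a cheap improvement. It costs SAP wording, chart extraction of failure status and steroid dose for treated patients at a single centre, and a small loss of power (0.952 to 0.938 at HR 0.5 and 0.763 to 0.738 at HR 0.65, with an assumed added R-squared of 0.10).

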The ultimate goal of this accrual expansion and survival comparison is to determine whether PVSRIPO administered at dose level -1 and, as needed, with a radiation-necrosis dose level and schedule of bevacizumab in the manner described within this protocol has merit for further evaluation in additional clinical studies. This goal is analogous to that of a randomized phase II screening study, except for the fact that the two groups are not created by randomization. The second historical control group will be considered in this comparison. Typically, with a randomized phase II study, there is a need to constrain the sample size requirements at the expense of either an increased false negative or false positive rate. It has been recommended that a false-positive rate of 0.2 be used to test a hypothesis comparing arms while maintaining a high power level (e.g. 90%).

A total of 50 subjects will be accrued and treated at dose level -1. Assuming survival is exponentially distributed and the median survival associated with the -1 dose level is 15.2 months, we anticipate that approximately 15 of the 50 patients will be deceased by the time accrual is complete in June 2016. Without additional follow-up, the power of a logrank test conducted at the 0.2 level of significance (one-tailed) to detect a hazard ratio of 0.5, 0.55, 0.6, and 0.65 are 0.95, 0.91, 0.84, and 0.76, respectively. Tabulated below is the power to detect these hazard ratios as a function of the number of additional months of follow-up after accrual completion (Table 4).

Follow-	Expected # Dead if Median OS = 15.2 months	Power of Comparison to Detect Noted Hazard Ratio						
up (Months)		Hazard Ratio = 0.5	Hazard Ratio = 0.55	Hazard Ratio = 0.6	Hazard Ratio = 0.65			
0	15	0.95	0.91	0.84	0.76			
1	16	0.96	0.92	0.85	0.78			
2	18	0.97	0.93	0.88	0.80			
3	19	0.97	0.94	0.89	0.81			
4	21	0.98	0.95	0.90	0.83			
5	22	0.98	0.96	0.91	0.84			
6	23	0.98	0.96	0.91	0.85			
7	24	0.99	0.96	0.92	0.85			
8	26	0.99	0.97	0.93	0.87			
9	27	0.99	0.9	0.94	0.87			
10	28	0.99	0.97	0.94	0.88			
11	29	0.99	0.98	0.94	0.89			
12	30	0.99	0.98	0.95	0.89			

Table 4. Power of the survival comparison to detect the noted hazard ratios

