#### 14.3.2. Dose Expansion at Dose Level -2

As described in section 11.3.8, this protocol is amended to reduce the PVSRIPO dose to dose level -2 (1.0 X 10^7 TCID50) with the goal of limiting the occurrence of undesirable burden from the inflammation and its treatment on as many subjects (including caregivers) as possible. Based upon additional animal studies, we are confident that dose level -2 (1.0 X 10^7 TCID50) will be a therapeutic dose. This amendment is not due to concerns for the safety of the patients on dose level -1, but due to the observation that less inflammatory reaction is a predictor of better survival and treatment response.

Twenty-seven (27) patients will be accrued to the dose expansion at dose level -2. The ultimate goal of this accrual expansion is to determine whether PVSRIPO administered at dose level -2 has merit for further evaluation in additional clinical studies. The second historical control group as described in Appendix 18.4 and section 14.3.1 will be to make this assessment.

A false-positive rate of 0.2 will be used to test a hypothesis comparing dose level -2 with the historical control group while maintaining a high power level (e.g. 90%). The rationale is provided in section 14.3.1.

Given that recently reported studies of effective immunotherapeutic agents show (1) delayed antitumor effects and hence delayed separation of survival curves, and (2) a percentage of patients who are "cured" or survive for a relatively long period of time, we will focus on long-term survivorship at a specific time point (i.e. 24 months). Within the second historical control group, the 24-month survival probability is 13.5%. Assuming 27 patients in the historical group, simulation studies show that a two-tailed chi-square test ( $\alpha$ =0.2) conducted to compare the proportion of patients alive at 24 months at the 0.2 level has 88.7% power to detect an increase to 35% in 24-month survival. Logistic regression will be used to adjust for confounding factors.

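### Section 14.3.1 leaves open a move from the Cox/log-rank test to 18- or 24-month survival without a rule, and its >84% milestone power does not fit a two-tailed test of 50 against 104

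*Combined protocol and SAP*

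**What the plan says.** Section 14.3.1 treats the level -1 expansion as a screening comparison with the second historical control group (104 patients, 103 deaths). On the error rate it says: "It has been recommended that a false-positive rate of 0.2 be used to test a hypothesis comparing arms". The sample size of 50 is justified by "the power of a logrank test conducted at the 0.2 level of significance (one-tailed) to detect a hazard ratio of 0.5" and by further hazard ratios in Table 4. Because the groups are not randomized, it adds: "Hence, survival comparisons will be conducted using the Cox model", with a list of adjustment covariates.

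The section then raises delayed effects and long survivors as reported for other immunotherapies and says: "If that is the situation with PVSRIPO, the power calculations and planned analyses may not be appropriate". The alternative is tentative: "It might be more appropriate to focus on long-term survivorship at a specific time point such as 18 and 24-month survival". Control survival is given as 23.1% at 18 months and 13.5% at 24 months. The milestone test is a two-tailed chi-square, described as follows: "conducted to compare the proportion of patients alive at 18 or 24 months at the 0.2 level has >84% power to detect an increase". The gain in question is 15%.

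For level -2, Section 14.3.2 cites the same immunotherapy experience but commits itself: "we will focus on long-term survivorship at a specific time point (i.e. 24 months").

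**The concern.** Three tests are in play for level -1: Cox/log-rank, 18-month survival and 24-month survival. Cox is the default. The condition for leaving it refers to how survival behaves with PVSRIPO, and the section does not say who judges this, when, or by what criterion. It also does not say which milestone would replace Cox, and the sidedness changes with the move.

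A 0.2 false-positive rate belongs to one test chosen in advance. If the test can be chosen once results are known, the rate for the whole procedure exceeds 0.2, and a reader of the final report cannot tell which situation applied. The analysis time is open as well: Table 4 runs from 0 to 12 months after accrual ends. Anyone treated in the last year of accrual would then have less than 24 months of follow-up, so a log-rank result could come first and the milestones later.

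The milestone power matters separately, because it is the justification offered for the fallback analysis.

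**Working it through.** **Inputs from Sections 14.3.1 and 14.3.2.** 50 treated; 104 controls with 103 deaths; 15 treated deaths expected at end of accrual; control survival 23.1% (18 months) and 13.5% (24 months); alpha 0.2, one-tailed for log-rank and two-tailed for chi-square. The stated increase of 15% is read as 15 percentage points.

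**Step 1: reproduce the plan's log-rank power.** Schoenfeld's formula is power = Φ(√(D·p·(1−p))·|ln HR| − z). Here D = 15 + 103 = 118, p = 15/118 and one-tailed z = 0.842. Then D·p·(1−p) = 15 × 103/118 = 13.09, with square root 3.618.
- HR 0.50: Φ(3.618 × 0.693 − 0.842) = 0.952 (plan 0.95)
- HR 0.55: 0.907 (plan 0.91)
- HR 0.60: 0.843 (plan 0.84)
- HR 0.65: 0.763 (plan 0.76)

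The plan's figures reproduce, which confirms that this test is one-tailed with control deaths counted.

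**Step 2: milestone power.** For two proportions, power = Φ((0.15 − z·√(p̄(1−p̄)(1/104 + 1/50))) / √(p0(1−p0)/104 + p1(1−p1)/50)), with two-tailed z = 1.282.
- 24 months: p0 = 0.135, p1 = 0.285, p̄ = (14.04 + 14.25)/154 = 0.184. Power = Φ((0.15 − 1.282 × 0.0666)/0.0721) = 0.815.
- 18 months: p0 = 0.231, p1 = 0.381, p̄ = (24.02 + 19.05)/154 = 0.280. Power = Φ((0.15 − 1.282 × 0.0772)/0.0802) = 0.738.

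| Test, 15-point gain | 18 months | 24 months |
|---|---|---|
| Two-tailed 0.2, normal approximation | 0.738 | 0.815 |
| Two-tailed 0.2, exact enumeration of Pearson chi-square | 0.745 | 0.823 |
| One-tailed 0.2, normal approximation | 0.856 | 0.904 |
| One-tailed 0.2, exact | 0.855 | 0.909 |
| Two-tailed 0.2, control rate treated as fixed, n = 50 | 0.858 | 0.916 |

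The stated >84% is met in the last three rows, not in the first two, which match the test described.

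**Step 3: false-positive rate under free choice.** Trials were simulated with no effect: 104 against 50, exponential survival with 13.5% alive at 24 months, an unadjusted log-rank test standing in for Cox, and complete milestone follow-up. Only findings of benefit count. A two-tailed 0.2 milestone test then contributes about 0.105 to 0.11.
- Log-rank alone, one-tailed 0.2: 0.19 to 0.20.
- Any of the three favourable, treated follow-up 24 to 48 months: 0.23 to 0.24.
- Any of the three favourable, follow-up 12 to 32 months: 0.234.
- Any of the three favourable, log-rank at end of accrual (follow-up 0 to 20 months) and milestones later: 0.266.

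If the tests were independent, the rate would be 1 − 0.8 × 0.9 × 0.9 = 0.352. With full follow-up they correlate at 0.73 to 0.83, which is why the excess is smaller.

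**Step 4: what removes the excess.** A single 24-month test gives 0.20 one-tailed, or 0.203 two-tailed (0.108 towards benefit). Switching by one fixed proportional-hazards test gives 0.18 to 0.22. Keeping all three tests would need about 0.10 to 0.12 one-tailed each.

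**The case against.** The strongest reply is that Cox is named as the planned analysis and the milestone text is only a caveat. The document nowhere says that the choice follows inspection of the curves. Section 14.3.2 shows that such a choice can rest on published experience with other agents. The excess is three to seven points and requires free choice of the favourable test. Efficacy is a secondary objective, and Section 14.2 says that no specific hypothesis is tested for secondary objectives. Section 11.3.11 records that level -1 had already been taken forward to phase II on pre-clinical data, bevacizumab need and toxicity.

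Much of this stands, and it limits the point. It does not close the gap: Section 14.3.1 does set a test with an alpha, and its condition is how PVSRIPO survival behaves, with no earlier decision point named.

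Some stronger readings are tempting but unsupported:
- A reader might infer a false-positive rate above 0.30. Running all three tests one-tailed at 0.2 would give 0.31 to 0.35, but the plan makes the milestones two-tailed. Using either milestone two-tailed gives about 0.31 only if findings of harm are counted; for benefit it is about 0.16.
- A reader might infer that no analysis is named, or that the plan expects delayed effects. It names Cox, and it says that delayed effects may occur.
- A reader might infer a wrong decision to proceed. Section 11.3.11 shows that this decision rested on other grounds.

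**Conclusion.** The point holds as a gap in pre-specification with modest inflation, together with a power figure that does not match its stated test. Under free choice the false-positive rate for benefit is about 0.23 to 0.24 at the levels as written, and about 0.27 with an early log-rank test, against 0.20. These rates assume exponential survival, the follow-up ranges shown (which are not in the documents), an unadjusted log-rank test in place of the adjusted Cox model, and no confounding.

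The power finding rests on fewer assumptions. For a two-tailed 0.2 chi-square test of 50 against 104, power for a 15-point gain is about 74% at 18 months and 82% at 24 months. The documents do not show whether the source is a sidedness label or a control rate treated as known.

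The consequence is a weaker efficacy claim from a secondary, non-randomized screening comparison. The primary dose-finding objective is unaffected.

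**What to change.** In Section 14.3.1:
- Name one decisive level -1 analysis, with its time point, sidedness and analysis date. Survival at 24 months would match Section 14.3.2. Make the remaining analyses supportive.
- Restate the power for that test: at 24 months about 82% two-tailed or 91% one-tailed; at 18 months about 74% or 86%. If the control rate was treated as fixed, say so and justify it.
- State which level -1 survival data had been seen when the choice was fixed. Sections 11.3.5 and 11.3.8 already report deaths and individual survival times at this dose level, so naming a test now does not by itself restore a clean 0.2.

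The cost is a wording change and a slightly less favourable stated power if the test stays two-tailed. No patients or procedures are added.

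### Section 14.3.1: a two-tailed chi-square test at 0.2 does not have the stated >84% power at 18 months (about 74%); either the sidedness label or the power figure needs correcting

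*Combined protocol and SAP*

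**What the plan says.** Section 14.3.1 sizes the dose level -1 expansion (50 patients) on a logrank comparison with the second historical control group (104 patients), one-tailed at 0.2. It then allows that exponential survival and proportional hazards may fail for an immunotherapy, and suggests that survivorship at a fixed time might be more suitable. For the second control group, "the 18 and 24-month survival probabilities are 23.1% and 13.5%, respectively". The test is introduced as "A two-tailed chi-square test" with alpha 0.2, applied to the proportions alive at 18 or 24 months, which "at the 0.2 level has >84% power to detect an increase of 15% in survivorship". Logistic regression is to adjust for confounders.

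Section 14.3.2 describes the dose level -2 test in nearly the same words. It is two-tailed at 0.2, is applied at 24 months only, and "has 88.7% power to detect an increase to 35% in 24-month survival". The sentence giving this figure assigns 27 patients to the historical group, although the section says that 27 patients will be treated and that the second historical control group is the comparator.

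**The concern.** A two-tailed test at 0.2 rejects at |z| > 1.282; a one-tailed test at 0.2 rejects at z > 0.842. The power figure and the label must refer to the same threshold, and here they do not appear to. Two things follow. A reader of a non-significant 18-month result would believe that the chance of missing a 15-point gain was under 16%, when for the test as labelled it is about 26%. And a favourable result with a one-sided p-value between 0.1 and 0.2 would count as positive or not depending on whether the analyst follows the label or the test that the power seems to describe.

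**Working it through.** **Inputs.** From Section 14.3.1: treated n = 50; controls n = 104 (second historical group); control survival p1 = 0.231 (18 months) and 0.135 (24 months); alpha = 0.2. The increase is read as 15 percentage points, so p2 = 0.381 and 0.285. A relative 15% is ruled out: it gives power of only 21% and 18% two-tailed, or 36% and 31% one-tailed (pooled approximation).

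**Formula** (uncorrected Pearson test, normal approximation):

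power = Φ[(0.15 − z·s0)/s1], where s0 = √{p̄(1−p̄)(1/104 + 1/50)}, s1 = √{p1(1−p1)/104 + p2(1−p2)/50} and p̄ = (104·p1 + 50·p2)/154.

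- 18 months: p̄ = 0.2797, s0 = 0.0772, s1 = 0.0802.
- 24 months: p̄ = 0.1837, s0 = 0.0666, s1 = 0.0721.

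**Reproducing the stated figure: one-tailed, z = 0.842.**

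- 18 months: (0.15 − 0.0650)/0.0802 = 1.060, power 85.6%.
- 24 months: (0.15 − 0.0561)/0.0721 = 1.303, power 90.4%.

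Both exceed 84%.

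**The test as labelled: two-tailed, z = 1.282.**

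- 18 months: (0.15 − 0.0990)/0.0802 = 0.636, power 73.8%.
- 24 months: (0.15 − 0.0854)/0.0721 = 0.896, power 81.5%.

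**Cross-checks.** Exact power sums the binomial probabilities of every possible table that rejects.

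| Calculation | 18 months | 24 months |
|---|---|---|
| Two-tailed, 50 v 104, exact | 74.5% | 82.3% |
| Two-tailed, unpooled variance | 72.2% | 78.8% |
| Two-tailed, continuity-corrected, exact | 67.5% | 76.5% |
| Two-tailed, first control group (124), exact | 75.8% | 83.6% |
| Two-tailed, control counts held at 24/104 and 14/104 | 77.0% | 88.2% |
| One-tailed, 50 v 104, exact | 85.5% | 90.9% |
| One-sample two-tailed, historical rate fixed, exact binomial | 85.0% | 88.2% |
| One-sample two-tailed, historical rate fixed, normal | 85.8% | 91.6% |

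No two-tailed comparison of the two groups in the table reaches 84% at 18 months.

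**Section 14.3.2, 24 months, 13.5% to 35%, alpha 0.2.**

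| Groups | Two-tailed, pooled | Two-tailed, exact | One-tailed, exact |
|---|---|---|---|
| 27 v 104 | 86.7% | 87.7% | 93.8% |
| 27 v 27 | 71.9% | 73.5% | 86.4% |

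With the control count held at 14/104, the two-tailed figure for 27 treated patients is 88.5%. The stated 88.7%, which the plan says was simulated, is therefore close to 27 treated against 104 controls, two-tailed. It is not close to 27 against 27.

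**The case against.** The best defence is that the power is right and only the label slipped. The logrank test in the same section is one-tailed at 0.2, and a one-tailed milestone test gives 85.5% and 90.9%. This is plausible and may well be the origin of the figure. It does not remove the inconsistency, but it does mean that the power itself cannot simply be called wrong.

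A second defence is that the historical rate was treated as a known benchmark. A two-tailed one-sample test then also exceeds 84% at both times. This fits the text poorly. The plan compares proportions with a 104-patient group and adjusts by logistic regression, which needs the control patients' data. For the survival comparison it also cites an unconditional estimator resembling that of a two-arm trial.

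A third point is that the 24-month shortfall is small: 1.7 points by the exact calculation, and none if the observed control count is held fixed. That stands, and the numerical case rests on 18 months.

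It is also fair to say that little hangs on the figure operationally. The 50-patient sample size comes from the logrank calculation and Table 4. Section 11.3.11 records the decision to take dose level -1 into phase II, and Section 16.6 gives closure of enrolment in June 2017. Correcting the power affects how the result is read, not the size of the trial or that decision.

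**Conclusion.** In Section 14.3.1 the two-tailed label and the >84% power cannot both stand. As labelled, the test has about 74% power at 18 months, a miss rate of about 26% against the implied figure of under 16%, and about 82% at 24 months, which is marginally short. With 104 controls and a two-tailed test, 84% power by the pooled approximation would need about 91 treated patients (18 months) or 58 (24 months). With 50 treated, it would need an increase of about 18 or 16 points. These figures assume an unadjusted test, an absolute 15-point increase, and known 18- and 24-month status for all 50 patients.

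Some stronger readings are tempting but not supported:

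- **That the plan expects non-proportional hazards at dose level -1, so the go/no-go decision rests on this test.** Section 14.3.1 raises this only as a possibility.
- **That the milestone powers in 14.3.1 and 14.3.2 were computed for different tests.** The reproductions suggest it, but it is inference, and the 14.3.2 match itself requires departing from that section's stated 27 historical patients.
- **That the false-positive rate is inflated across the logrank, 18-month and 24-month tests.** This needs a rule that any one positive test suffices, which the plan never states.
- **That a two-tailed 0.2 test, with about 0.1 in the favourable direction, is an error.** The rationale for 0.2 does not state its sidedness, and two-tailed is simply the more conservative choice.

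**What to change.** In Section 14.3.1, do one of the following:

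1. Keep the two-tailed test and restate the power as about 74% (18 months) and 82% (24 months).
2. Declare the milestone test one-tailed at 0.2, in line with the logrank test, and state about 85% and 91%.

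In either case, say that the increase is 15 percentage points and that the power allows for sampling variability in the 104 controls. Use the same sidedness in Section 14.3.2; if one-tailed is chosen, the figure there becomes about 94% for 27 against 104. Also in 14.3.2, correct the sentence that puts 27 patients in the historical group, so that it gives 27 treated against 104 controls.

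The original calculation record, if available, should settle which option is the correction. Survival outcomes at dose level -1 were already reported in Section 11.3.8, so the clarification should be dated and its reason given. For the same reason, this point is not grounds for promoting 24-month survival to sole deciding test or demoting the Cox model: the arithmetic does not require it, and it would change the analysis hierarchy after outcomes were known.

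The cost is a few sentences in Section 14.3 and, if two-tailed is kept, a less favourable stated power. Sample size and data collection are unaffected.
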